 - Fondaparinux will be supplied as solution for SC injection in pre-filled syringes (2.5 mg/0.5 mL, 5.0 mg/0.4 mL, 7.5 mg/0.6 mL, 10.0 mg/0.8 mL, and where available 1.5 mg/0.3 mL).

- Warfarin will be supplied as tablets (0.5 mg, 1.0 mg, and 3.0 mg).

For subjects in whom clinicians prescribe warfarin, then warfarin will be started on Day 1. Heparin (enoxaparin or fondaparinux or UFH depending on the therapy received during pre-randomization period) will be discontinued when INR ≥ 2.0 and ≤ 3.0 for 2 consecutive measurements obtained at least 24 to 48 hours apart. The subject will continue warfarin for the remainder of the study treatment period.

Study Endpoints:

All safety and efficacy endpoints described below will be adjudicated in a blinded manner by the Clinical Events Committee (CEC).

Primary Efficacy Endpoint:

The primary efficacy endpoint is a composite endpoint consisting of the incidence of symptomatic recurrent venous thromboembolic disease, death as a result of VTE, and no change or extension of thrombotic burden (Section 7.1) during the first 3 months period.

-For subjects in Cohort 5, (ie, <6 months old), the primary efficacy endpoint is a composite endpoint consisting of the incidence of symptomatic recurrent VTE, death as a result of VTE, and no change or extension of thrombotic burden within 6 to 12 weeks + 3 days.

Secondary Efficacy Endpoints:

The secondary efficacy endpoints include:

- A composite endpoint consisting of symptomatic recurrent venous thromboembolic disease, death as a result of VTE, and no change or extension of thrombotic burden from randomization to the date of the last dose of study drug + 30 days .
- The individual components of the primary efficacy endpoint during the first 3-month period (for Cohort 5, the intended duration of treatment is 6-12 weeks):
 - Symptomatic recurrent VTE
 - Death as a result of VTE
 - No change or extension of thrombotic burden
- All-cause mortality from randomization to last dose + 30 days.

- The DVT, Catheter-related thrombosis, PE, sinovenous thrombosis events within and after the first 3-month treatment period (for Cohort 5, the intended duration of treatment is 6-12 weeks).

Net Clinical Outcome Endpoint:

- Composite of symptomatic recurrent VTE events, death as a result of VTE, and major and CRNM bleeding that occurred from the date of the first dose of study drug to the date of last dose of study drug + 30 days.

Safety Endpoints:

The safety endpoints are:

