Statistical Analyses:	
Analysis Sets:
 
Randomized Analysis Set will include all subjects who are randomized.
 
Safety Analysis Set will include all subjects in the Randomized Analysis Set who received at least one dose of study drug actually taken.
 
Modified intent-to-treat (mITT) Analysis Set will include all subjects in the Randomized Analysis Set who received at least one dose of randomized study drug.
 
Per-protocol (PP) Set will include all subjects in the mITT Analysis Set who are sufficiently compliant with the protocol. Criteria of sufficiently compliant will be detailed in SAP.
 
PK Analysis Set will include all subjects in the Safety Analysis Set who had at least one PK sample with measurable concentration.
 
PD Analysis Set will include all subjects in the Safety Analysis Set who had at least one measurable PD sample.
 
Efficacy Analyses:
 
Primary Efficacy Analyses:
 
The primary efficacy endpoint is a composite endpoint, including symptomatic recurrent venous thromboembolic disease, death as result of VTE, and no change or extension of thrombotic burden based on imaging during the first 3-month treatment period (ie, primary efficacy events occurring from randomization through the end of the 3-month treatment period). For subjects in Cohort 5, (ie, <6 months old), the primary efficacy endpoint is a composite endpoint consisting of the incidence of symptomatic recurrent VTE, death as a result of

VTE, and no change or extension of thrombotic burden within 6 to 12 weeks + 3 days. The primary efficacy analysis will be based on mITT Analysis Set. Analyses will be based on the randomized treatment even if a subject inadvertently receives the incorrect study drug.

In this analysis, the time to the first event of the composite primary efficacy outcome will be analyzed using a Cox's proportional hazard regression model including treatment and age groups as covariates.

The edoxaban-to-comparator hazard ratio will be computed with 95% confidence interval [CI] (two-sided) based on this model.

Edoxaban will be considered non-inferior to comparator if the upper limit of the 95% CI is <1.5.

If non-inferiority of edoxaban is established, edoxaban will be tested for superiority to comparator. Edoxaban will be considered superior to comparator if the upper limit of the 95 % CI from above analysis is <1.0.

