9.2. Safety Endpoint Event(s)

All potential safety endpoints will be adjudicated by an independent CEC. Study endpoints and safety data will be periodically reviewed by an IDMC to ensure the safety of study participants.

The safety related secondary objectives are:

- To compare edoxaban against SOC with regard to the combination of major and CRNM bleedings occurring during treatment or within 3 days of completing or interrupting or stopping study during the first 3-month treatment period (for Cohort 5, the intended duration of treatment is at least 6 to 12 weeks).
- To compare edoxaban against SOC with regard to all bleedings which occur from first to the last dose + 30 days.
- To compare edoxaban against SOC with regard to a composite combination of major and CRNM bleedings from first to the last dose + 30 days.

The corresponding safety endpoints are:

- A combination of major and CRNM bleedings occurring during treatment or within 3 days of completing or interrupting or stopping study during the first 3-month treatment period. For subjects in Cohort 5, ie,<6 months old, the primary safety endpoint, is a combination of major and CRNM bleedings occurring during treatment or within 3 days of completing or interrupting or stopping study within 6 to 12 weeks period + 3 days.
- All bleedings from first to the last dose + 30 days.
- A combination of major and CRNM bleedings from first to the last dose + 30 days

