11.4.1. Efficacy Analyses

11.4.1.1. Primary Efficacy Analyses

The primary efficacy analysis will be based on mITT Analysis Set. Analyses will be based on the randomized treatment arm even if a subject inadvertently receives the incorrect study drug. The primary efficacy endpoint is an event driven and a composite endpoint including symptomatic recurrent venous thromboembolic disease, death as result of VTE, and no change or extension of thrombotic burden from randomization to up to 3 months + 3 days from randomization. In this analysis, the time to the first event of the composite primary efficacy outcome will be analyzed using a Cox's proportional hazard regression model including treatment arm and age groups as covariates. Although this study is also stratified by region, region is not included in the model as a covariate because some age groups within regions may be very small due to the small overall sample size. The time to first event is defined as the time (days) from the day of randomization to the first event experienced by a subject during the 3 months + 3 days period. Subjects who did not have a primary efficacy outcome during the 3 months + 3 days period will be censored at 3 months + 3 days or the last day the subject had a complete assessment for study outcomes, whichever comes first. The edoxaban-to-comparator hazard ratio will be computed with 95% confidence interval (CI) (two-sided) based on this model. Edoxaban will be considered non-inferior to comparator if the upper limit of the 95% CI is ≤ 1.5 .

If non-inferiority of edoxaban is established, edoxaban will be tested for superiority to comparator. Edoxaban will be considered superior to comparator if the upper limit of the 95% CI from above analysis is ≤ 1.0 .

To control study-wise type I error, the testing for non-inferiority and superiority will follow the plan as described below.

The same proportional hazard model used for primary efficacy analysis will be performed for PP Analysis Set and Randomized Analysis Set as sensitivity analyses.

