11.4.3.1. Analysis of bleeding events

An analysis will be performed for the composite safety endpoint of major and CRNM bleeding events which occur on-treatment from the first dose of study drug to 3 months + 3 days, or to the last dose of the study drug + 3 days if the subject permanently discontinued study drug prior to Month 3. The analysis of this endpoint is based on an “on treatment” approach. An event will be considered as an “on-treatment” event if it occurred while on study drug or within 3 days of randomized study drug interruption or discontinuation.

The time to “on-treatment” major and CRNM bleeding will be compared between treatment arms for subjects in the Safety Analysis Set, using the same Cox proportional hazards regression model as used for the primary efficacy analysis. Subjects who did not have an event will be censored at 3 days after the day of permanent study treatment discontinuation, or at 3 month + 3 days, or 6 to 12 weeks for Cohort 5, whichever occurred first.

Similar analyses will be conducted for all bleeding, as categorized below, occurred from the date of the first dose of study drug to the date of the last dose of study drug + 30 days using the Safety Analysis Set. Subjects who did not have corresponding event will be censored 30 days after the day of permanent study drug discontinuation.

Bleeding events will be summarized and analyzed for the following categories:

- Major and CRNM bleeding combined
- Any bleeding (major, CRNM, and nuisance, combined)

A sensitivity analysis will be conducted for major and CRNM bleeding, occurring while on-treatment, from the date of the first dose of study drug to the date of the last dose of study drug + 3 days during the whole study period. Subjects who did not have corresponding event will be censored 3 days after the day of permanent study drug discontinuation.

The incidence of bleeding events will also be summarized by treatment arm for on-treatment period up to 3 months + 3 days, on-treatment up to the date of last dose of study drug + 3 days, and from the date of the first dose of study drug to the date of the last dose of study drug + 30 days, using Safety Analysis Set.

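### Sections 11.4.1.1 and 11.4.3.1 do not carry the Cohort 5 endpoint window into the analysis, so event counting and censoring in the youngest infants are inconsistent

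*Combined protocol and SAP*

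**What the plan says.** **Endpoint definitions.** The synopsis gives Cohort 5 its own primary efficacy window, "no change or extension of thrombotic burden within 6 to 12 weeks + 3 days", and repeats it in its statistical text on the primary analysis. Section 9.2 gives the matching bleeding endpoint: "occurring during treatment or within 3 days of completing or interrupting or stopping study within 6 to 12 weeks period + 3 days". The synopsis safety endpoints say the same.

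**Primary analysis.** Section 11.4.1.1 describes the composite as including "no change or extension of thrombotic burden from randomization to up to 3 months + 3 days from randomization". It measures time to first event over that same period, and event-free subjects are "censored at 3 months + 3 days or the last day the subject had a complete assessment for study outcomes", whichever is earlier. It has no Cohort 5 rule.

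**Bleeding analysis.** Section 11.4.3.1 counts on-treatment major and CRNM bleeds from "first dose of study drug to 3 months + 3 days, or to the last dose of the study drug + 3 days", the second limit applying to those who stop permanently before Month 3. No Cohort 5 limit appears there. Event-free subjects are censored 3 days after permanent discontinuation, "or at 3 month + 3 days, or 6 to 12 weeks for Cohort 5, whichever occurred first".

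**Related text.** Sections 3.2 and 6.3 end the Cohort 5 Main Treatment Period when the infant's own anticoagulant therapy ends. Section 6.3.3 follows Cohort 5 subjects who interrupt or stop drug to Month 3 or to an earlier point at 6 to 12 weeks. Section 7.1 gives both ±5 and ±3 days for the thrombotic-burden image.

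**The concern.** The window decides which events enter the primary and bleeding analyses and how long each infant is at risk. Two parts of the protocol answer this differently for the primary endpoint. For bleeding, the events and the censoring follow different rules within one section.

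A Cox model needs the same observation period for events and for time at risk. If an infant's bleed counts up to one date while event-free infants leave the risk set sooner, the later events are set against a risk set that omits infants who were still on treatment.

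Imaging adds to the efficacy problem, because an unchanged thrombus is itself an event. Sections 6.3.1 and 6.3.3 allow an image at week 6, and Section 6.3.1 describes another after week 12. A thrombus unchanged at week 6 but smaller at week 12 is an event or not depending on which image closes the window, and nothing in the text settles this.

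The trial is open-label (Section 3.1), and Section 11.7 requires the SAP to be final only before database lock. The choice should not wait until data have accrued.

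**Working it through.** **Design figures first.** The inputs from Section 11.6 are a margin of 1.5, an assumed hazard ratio of 0.76, two-sided alpha 0.05, 80% power and 1:1 allocation.
- Schoenfeld events = 4 × (1.960 + 0.842)² / [ln(1.5/0.76)]² = 67.9, so 68. Power with 68 events is 80.0%.
- With 28% control risk, 68 / mean risk gives 276 subjects if the 24% is a risk reduction (28% and 21.28%), or 271.5 if it is a hazard ratio (28% and 22.09%). The plan's 274 lies between them. Nothing below changes these figures.

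**Day counts.** 6 weeks = 42 days and 12 weeks = 84 days. Three months is taken as 90–92 days, so 3 months + 3 days = 93–95. First dose is assumed to fall on the day of randomization.

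**Primary efficacy window**
- 6-week course: synopsis 42 + 3 = 45 days; Section 11.4.1.1 up to 93–95 days. The excess is 48–50 days, about 2.1 times the window (93/45 = 2.07).
- 12-week course: synopsis 84 + 3 = 87 days; Section 11.4.1.1 up to 93–95 days. The excess is 6–8 days (7–9%).
- Example: Table 17.1, note b, puts the follow-up visit one month after completion, about day 42 + 30 = 72 for a 6-week infant. A recurrent VTE on day 60 counts under Section 11.4.1.1 but lies outside the 45-day window.

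**Bleeding analysis: last day on which each rule applies**

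| Course | Endpoint (9.2) | Events counted (11.4.3.1) | Event-free censored, range = own duration | Event-free censored, range = lower end |
|---|---|---|---|---|
| 6 weeks, then stops | 45 | 45 | 42 | 42 |
| 12 weeks, then stops | 87 | 87 | 84 | 42 |
| 12 weeks, then extension | 87 | 93–95 | 84 | 42 |

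- 12-week infant, own duration: 3/87 = 3.4% of follow-up lost.
- 12-week infant, lower end: (87 − 42)/87 = 45/87 = 52% lost.
- 6-week infant on either reading: 3/45 = 6.7% lost. If the range were instead read as its upper end, discontinuation + 3 days comes first and nothing is lost.
- Each row with a gap between the third column and the last two shows days on which an event counts although event-free infants have been censored.

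**Trial level.** Total Cohort 5 size is not stated. Section 6.3.1 gives 5 to 12 edoxaban infants for the PK assessment; doubling for 1:1 allocation gives an assumed 10–24, or 3.6–8.8% of 274. Suppose all are treated for 12 weeks, are event-free and are censored at week 6, and other subjects contribute 93 days:
- 10 infants: 10 × 45 / (10 × 87 + 264 × 93) = 450/25,422 = 1.8%.
- 24 infants: 24 × 45 / (24 × 87 + 250 × 93) = 1,080/25,338 = 4.3%.

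**The case against.** **The range need not mean week 6.** A reader might infer that the first-to-occur wording fixes censoring at week 6 and discards half the follow-up of a 12-week infant. The text does not say so. That phrase chooses among the three listed limits, not within the range. The reading closest to Section 6.3 is the infant's own treatment duration, which costs 3 days. The 52% is only the worst case.

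**Bleeds after week 6 are not excluded.** A reader might also infer that such bleeds drop out. Section 11.4.3.1 censors only infants without an event, and its event definition still counts a week-8 bleed on treatment. The bleed would be lost only if the censoring date were also programmed as an event cutoff. Other analyses in that section run to last dose + 3 days over the whole study and to last dose + 30 days. What remains is the mismatch between counting and censoring.

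**The 3 months + 3 days window is not uniform across the protocol.** The synopsis statistical text carries the Cohort 5 window, so this is an internal contradiction. The 93–95 days are also a ceiling: censoring at the last complete assessment and the earlier Cohort 5 end visit will often shorten it. They do not remove the conflict, as the day-60 example shows.

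**The SAP may settle it.** Section 11.7 leaves definitions to the SAP. No such text on this point is available for review, and the conflict within the protocol stands meanwhile.

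**Conclusion.** The inconsistency holds on the text and goes beyond missing detail. Following Section 11.4.1.1 counts events outside the Cohort 5 efficacy endpoint. Following Section 11.4.3.1 can count bleeds after event-free infants have left the risk set, and its censoring rule names no date.

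For an individual infant the effect can be large: up to about twice the intended efficacy window on a 6-week course, and between 3.4% and 52% of bleeding follow-up on a 12-week course. For the trial it is small: at worst about 2–4% of planned main-period follow-up, resting on an assumed 10–24 Cohort 5 infants and the least favourable reading. The sample size and event target are unaffected. It should be corrected because these infants have their own endpoint definition and the analysis does not yet use it.

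**What to change.** Define one subject-specific Cohort 5 analysis window and use it for both event counting and censoring in Sections 11.4.1.1 and 11.4.3.1:
- **Efficacy:** from randomization to the end of that infant's Main Treatment Period, at most 12 weeks, + 3 days. Event-free infants are censored then or at the last complete assessment, if earlier.
- **Bleeding:** from first dose to the same end point, or to permanent discontinuation + 3 days if that comes first. Change the event window as well as the censoring sentence; changing only the latter would leave an infant in the extension with events counted to day 93–95 and censoring at day 87.
- **Early stopping:** say how the efficacy window ends for an infant who stops early, since Section 6.3.3 keeps such infants under efficacy follow-up.
- **Imaging:** state which image, week 6 or week 12, defines the thrombotic-burden event, and reconcile the ±5 and ±3 day windows in Section 7.1. Until that is done, Section 7.1 cannot serve as the reference for Section 11.4.1.1.

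The cost is protocol and SAP wording. No visit, sample or subject is added.

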11.4.3.2. Adverse Event Analyses

Adverse events will be coded according to the Medical Dictionary for Regulatory Activities (MedDRA).

Treatment-emergent AEs (TEAEs) are defined as AEs that occur, having been absent before the initial of study treatment, or worsen in severity after the initiation of study treatment administration. Adverse events that start or worsen after the 30th day following the calendar date of the dose of the last study drug are defined as post-treatment AEs.

The incidence of TEAEs will be presented for the Safety Analysis Set for the on treatment period and from the date of the first dose of study drug to the date of the last dose of study drug, respectively, by System Organ Class, by preferred term, and by treatment arm. TEAEs will be

further summarized by relationship to the study drug, and by severity. Frequent TEAEs (reported by $\geq 5\%$ of subjects in any treatment arm) will also be summarized by treatment arm for the on-treatment period and from the date of the first dose of study drug to the date of the last dose of study drug, respectively. The incidence of death, SAEs, drug-related SAEs, and AEs leading to discontinuation of study drug will also be summarized. All AEs will be included in a data listing and a listing to display the coding of AEs will be prepared as well.

Similarly, the number and percentage of deaths, subjects reporting treatment-emergent SAEs, and TEAEs leading to discontinuation of study treatments will be tabulated.

A by-subject AE (including treatment-emergent) data listing including but not limited to verbatim term, preferred term, system organ class, preferred term, and relationship to study drug will be provided. Deaths, other SAEs, and other significant AEs, including those leading to discontinuation of study drug, will be listed.

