9. SAFETY EVALUATION AND REPORTING

9.1. Adverse Event Collection and Reporting

In the event of a Medical Emergency, the Investigator at the study site will institute any medical procedures deemed appropriate. A 24-hour Urgent Medical Contact will be provided to contact the Medical Monitor for further guidance.

Sites will receive a contact card where the following numbers (24-hour Urgent Medical Contact) are provided:

PPD [REDACTED] (primary number)

PPD [REDACTED] (alternative number)

The medical call center will contact Medical Monitor for the assigned region.

All AEs (see Section 9.4.1 for definitions) occurring after the subject signs the Informed Consent Form and up to 30 days after the last dose of study drug (ie, the Follow-Up Visit), whether observed by the Investigator or reported by the subject, will be recorded on the Adverse Event CRF page. Medical conditions (including laboratory values/vital signs that are out of range) that were diagnosed or known to exist prior to Informed Consent will be recorded as part of medical history.

All AEs, serious adverse events (SAEs), bleeding, and events of special interest are to be reported according to the procedures in Section 9.5.

All laboratory results and vital signs should be appraised by the Investigator to determine their clinical significance. Isolated abnormal laboratory results or vital sign findings should be reported as AEs if they are symptomatic, lead to study drug discontinuation, dose reduction, require corrective treatment, or constitute an AE in the Investigator's clinical judgment.

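### The general TEAE incidence tables have no window that reaches last dose + 30 days, although the same section implies that treatment emergence runs that far

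*Combined protocol and SAP*

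**What the plan says.** **Section 11.4.3.2 (Adverse Event Analyses)**

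- *Start of treatment emergence.* An event qualifies if it was absent before treatment and then occurs, "or worsen in severity after the initiation of study treatment administration". This sentence gives no end date.
- *Post-treatment events.* This class is set by timing: "start or worsen after the 30th day following the calendar date of the dose of the last study drug are defined as post-treatment AEs".
- *Tables.* Two periods are named. For the first, the text is: "The incidence of TEAEs will be presented for the Safety Analysis Set for the on treatment period". The second period runs "from the date of the first dose of study drug to the date of the last dose of study drug, respectively". Rates are shown for each arm, broken down by system organ class and preferred term. The same pair of periods is repeated for frequent TEAEs (at least 5% of subjects in any arm).
- *Other summaries.* The summaries of TEAEs by relationship and severity, and those of deaths, SAEs and events leading to discontinuation, state no period. All adverse events go into a listing.

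**Section 9.1** records adverse events from consent "up to 30 days after the last dose of study drug".

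**Section 11.4.3.1**, on bleeding, counts an event as on-treatment if it occurs on study drug or "within 3 days of randomized study drug interruption or discontinuation". It also has bleeding analyses and summaries that run from first dose to last dose + 30 days.

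**The concern.** Section 11.4.3.2 sets one boundary for treatment emergence and another for tabulating it. Taken with the post-treatment definition, days 1-30 after the last dose belong to the treatment-emergent period, and Section 9.1 ensures that events on those days are recorded. Neither period named for the two main table types reaches day 30. A programmer following the text would flag such events as treatment-emergent, list them, and leave them out of the by-arm incidence.

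These tables are where a reader looks first for an imbalance in general safety. The 5% rule for frequent TEAEs also depends on the window, so the period chosen can decide whether a preferred term is shown at all. The parallel bleeding text in Section 11.4.3.1 uses last dose + 30 days, which suggests that the extra 30 days were simply left out of the adverse-event sentences.

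**Working it through.** The plan gives no figure for this point, so there is none to reproduce. The check compares windows and then sizes the gap.

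**1. Windows side by side**

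| Item | Section | Ends at |
|---|---|---|
| Adverse event collection | 9.1 | last dose + 30 days |
| TEAE (implied by the post-treatment definition) | 11.4.3.2 | last dose + 30 days |
| TEAE tables, first period | 11.4.3.2 | end of on-treatment period, undefined for adverse events |
| TEAE tables, second period | 11.4.3.2 | last dose |
| On-treatment bleeding | 11.4.3.1 | last dose + 3 days, or 3 months + 3 days |
| Bleeding, longer window | 11.4.3.1 | last dose + 30 days |
| Secondary efficacy composite, all-cause mortality | 11.4.1.2 | last dose + 30 days |
| Net clinical outcome | 11.4.1.4 | last dose + 30 days |

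The second TEAE period never reaches day 30 after the last dose. The first does not either under any on-treatment rule found in the documents.

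**2. Share of the implied TEAE window left out**

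Let T be days on treatment, so that the implied window is T + 30 days.

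- Cut at last dose: 30/(T + 30).
- Cut at last dose + 3 days (bleeding rule borrowed): 27/(T + 30).

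| Treatment | T | Cut at last dose | Cut at + 3 days |
|---|---|---|---|
| 6 weeks (Cohort 5) | 42 | 30/72 = 41.7% | 27/72 = 37.5% |
| 12 weeks (Cohort 5) | 84 | 30/114 = 26.3% | 27/114 = 23.7% |
| 3 months | 90 | 30/120 = 25.0% | 27/120 = 22.5% |
| 12 months | 365 | 30/395 = 7.6% | 27/395 = 6.8% |

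These are shares of time, not of events.

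**3. Illustration in subjects (assumed rates)**

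The documents give no adverse event rates. Assume a constant hazard, 137 subjects per arm (Section 3.2), 90 days on drug and incidence p by the last dose. The count to last dose + 30 days is 137 × [1 − (1 − p)^(120/90)].

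| Assumed p | To last dose | To last dose + 30 days |
|---|---|---|
| 5% | 6.9 | 9.1 |
| 10% | 13.7 | 18.0 |
| 20% | 27.4 | 35.3 |

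For the 5% rule, the incidence at last dose that becomes 5% by day 30 is 1 − 0.95^(90/120) = 3.8%. Under this assumption, a term at 3.8-5% to last dose would be absent from the frequent-TEAE table with the written window and present with the longer one.

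**The case against.** **The tables are descriptive and a shorter window is defensible.** No hypothesis test rests on them. After stopping, a subject may move to another anticoagulant (Sections 3.2 and 17.5), so later events may reflect a different drug. This stands as a reason to keep an on-treatment table. It does not explain why a second table, set beside it, also stops short of the implied TEAE window.

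**The 30-day end is inferred.** This also stands. The TEAE sentence has no upper limit, and the 30 days come from the definition of post-treatment events. The inference is natural and agrees with Section 9.1, but the plan should state it.

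**Most of the important safety events are covered elsewhere.** Bleeding, all-cause mortality, the efficacy composite and net clinical outcome are analysed or summarized by arm to last dose + 30 days. The death, SAE and discontinuation summaries have no stated cut-off and could include the 30 days. A reader might infer that all events arising after stopping are lost to the comparison of arms. The documents do not support that: the loss is confined to the general TEAE and frequent-TEAE tables.

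**Two further inferences are tempting and unsupported.**

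- *That the second table is narrower than the first.* This needs the bleeding rule to define on-treatment for adverse events, and even then the periods are not nested. Section 5.3 allows interruptions of any length. A first-to-last-dose window includes events late in an interruption, which the 3-day rule excludes. If the cap of 3 months + 3 days applies, the second window is wider for subjects in the Extension Period.
- *That rates are understated more in the arm with more early stopping.* The omitted share does grow as treatment shortens, but the documents give no discontinuation rates by arm, so no direction of bias can be claimed.

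**Conclusion.** The mismatch is real and limited. As written, TEAEs that start on days 1-30 after the last dose (days 4-30 if the bleeding rule is borrowed) are collected and listed but enter neither of the two general by-arm incidence tables. The gap is 27-30 days per subject. It is largest, as a share, for short Cohort 5 courses (37.5-42% at 6 weeks), 22.5-25% for a 90-day course, and falls to about 7-8% at 12 months.

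This rests on reading the post-treatment definition as the end of treatment emergence. It also assumes that no other text sets a longer window for these tables. Section 11.7 refers further detail to the SAP, but nothing in the supplied documents closes the gap. How many events are affected cannot be said. The primary test, sample size and error control are untouched. It should be corrected before database lock.

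**What to change.** In Section 11.4.3.2:

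1. End the second period at last dose + 30 days, as Section 11.4.3.1 does for bleeding. Do this in both sentences: the system organ class/preferred term tables and the frequent-TEAE tables.
2. State in the TEAE definition that the window closes at last dose + 30 days.
3. Keep the on-treatment table beside it, and define on-treatment for adverse events. The definition should cover interruptions and say whether a 3-month cap applies.
4. State the period for the SAE, death and discontinuation summaries.

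The cost is a few lines of text and a date limit in the table programs, because the data are already collected under Section 9.1. The one small downside is that the longer window may include events after transition to another anticoagulant. The on-treatment table beside it separates those.
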